MARCH 1, 2019

**Evaluation of the Relationship
Between Vaginal, Placental and
Neonatal Mycobiota and Microbiome
with Preterm Birth in Women
with
Short Cervical Length**

[name]
KOC UNIVERSITY SCHOOL OF MEDICINE

STUDY PROTOCOL

Introduction

The term microbiota is used to describe "ecological commensal, symbiotic and pathological communities" living on and / or within all multicellular microorganisms, from plants to animals. Microbiota contributes to the immunological, hormonal and metabolic homeostasis of the host. As in all natural orifices in the body, there is also a microbiota and mycobiota specific to the vagina.

On the other hand, the sonographic short cervix in the second 3 months of pregnancy is associated with preterm delivery, which may be an important cause of mortality and morbidity in the neonatal period. American Society of Obstetricians and Gynecologists (ACOG), British Royal Society of Obstetricians and Gynecologists (RCOG) and the American Society of Maternal Fetal Medicine (SMFM) suggests the measurement of transvaginal sonographic cervical length at 20-24 gestational weeks for screening of preterm birth. Aforementioned associations also recommend the use of progesterone in the treatment of women who diagnosed with short cervix by transvaginal ultrasonography due to the fact that progesterone is effective in prevention of preterm birth (Grade B) (1-2).

Previous vaginal microbiota studies have shown that some bacterial species, such as *Lactobacillus insers*, cause a predisposition to premature labor in patients with short cervix (3). However, the prominent deficiency in these studies is that the eukaryotic fungi in abundant vaginal flora have not been evaluated.

On the other hand, it is already known that progesterone treatment is not able to prevent all preterm birth in women with short cervical length. As a research group, our hypothesis is that the variety of microbiological and / or mycobiotal in pregnancies resulting in preterm birth are different than those who give birth at term although patients with sonographic short cervical length receive progesterone regularly from the second trimester. In this study, the aim of this study is to evaluate the patterns of microbiota and mycobiota from vaginal swabs of women who had preterm birth due to sonographic short cervical length and postpartum swabs of placenta and fetal oral cavity.

In this study, it has already known that some species in vaginal flora present a greater risk for preterm delivery. Women with short cervical length tend to give preterm birth, especially in the second trimester of pregnancy (between 20-28 weeks of gestation). Babies born in this early period are exposed to high risk of morbidity, such as severe neurodevelopmental sequelae, even if they survive. Early diagnosis and appropriate treatment of cervical / vaginal mycobiota and microbiota changes in women with short cervical length might reduce the rate of preterm birth and the associated neonatal mortality and morbidity.

Yet, measurements of cervical length are routinely performed in all pregnant women at 11-14th and 18-22 th gestational weeks by transvaginal ultrasonography. Of these patients, cervical swabs will be obtained just before the scans from women who agree to participate in the study will be kept in the -80 closet in our hospital until the samples are studied. Study group will include women who had cervical length 25 mm or less than 25 mm at 20-24 th gestational week and underwent birth (preterm delivery) before 37 + 0 weeks of gestation. The control group had pregnancies with a cervical length above 25 mm and delivered at term (37 + 0 gestational week and above). During the follow-up of pregnancies, care will be taken not to use antibiotics. Plaques of placental tissue in sterile

conditions and oral swab samples from newborns will be taken from women whose follow-up and delivery are performed in our hospital and by our team.

The inclusion criteria are:

- Singleton pregnancies
- The pregnant women who are willing to participate sign the informed consent form

The exclusion criteria are:

- Multiple pregnancies
- The presence of fetal anomaly
- Finding the intrauterine mort de fetus
- Antibiotic and / or antifungal use at any time of pregnancy
- Pregnant women under 18 years of age
- Women with previous cervical surgery
- Women who do not accept to participate to be in the study
- The presence of uterine anomaly
- Women with vaginal bleeding at the time of cervical swabs taken

Study Procedure

The measurements of cervical length will be performed by the perinatology team in two different periods of pregnancy (11-14 and 18-22 weeks of gestation) in the singleton pregnancies. Firstly, the vaginal swabs of women who accept to participate in the study will be collected at 11-14th weeks of gestation just before the measurement of cervical length. Also, the vaginal swabs through the aforementioned procedure will be collected at

18-22 weeks of gestation. Micronized progesterone will be started in women with a cervical length equal or less than 25 mm (smaller than 3rd percentile) at 18-22 weeks of gestation. The medication (progesterone 200mg) will be administered intravaginally every night before bedtime and will continue until 36th gestational week unless the patient gives birth. Measurement of cervical length will be repeated transvaginally at 28th and 32nd gestational weeks, and samples will be taken with vaginal swab before these measurements. In order to evaluate the presence of placental mycobiota and microbiota after birth, 1 cm x 1 cm x 1 cm of tissue sample from placenta that is 3 cm lateral of the cord insertion will be taken under sterile conditions. In order to evaluate the amniotic compartment, buccal mucosal swabs will be taken from the neonates immediately after birth. All samples taken during pregnancy follow-up and after delivery will be delivered to our Research Laboratory immediately and will be kept and stored in -80 degrees cabinet until the evaluation.

Study population

The study will plan to take 2 years for recruitment of patients. The enrollment of 60 participants with singleton pregnancies who have cervical length of 25 mm or less would give the study a power of 85% to show a treatment effect at a two-sided alpha level of 5%. The risk of preterm birth in a pregnant with a cervical length of 25 mm or less is 30%. The rate of preterm birth is 12% in the whole population. Thirty-two women who delivered at term with cervical length of longer than 25 mm will be in the control group. For the recruitment of study group, 1429 women with singleton pregnancies will need to be screened.

The patients will be included in the study group;

- 1) Pregnant women with cervical length of 25mm or less (n=60)

A) Of 60 patients, 30% will be expected to give a birth before 37 gestational weeks (n=18)

B) Of 60 patients, almost 70% will be expected to give a birth at term (n=42)

2) As a control group, women with a cervical length of more than 25 mm who give a birth at term will be included (n=32)

A total of 1429 women will need to be screened to be able to recruit the above numbers of patients.

Analysis of Microbiota

Isolation of DNA

Genomic DNA will be stored at 80 0 C until the analysis microbiota is performed by using the BIO PowerSoil DNA isolation kit.

Bacterial microbiota

The V3-V4 regions by the 16s ribosomal RNA sequencing method will be sequenced with the Illumina MiSeq device and the data will be analyzed according to the protocols standardized in the Human Microbiome Project.

Fungal Microbiota

DNA samples which will be ranked from the data to be sequenced in accordance with the ITS1 region metabiota protocol will be evaluated within the Human Microbiome Project.

Pseudomonas, Escherichia, Neisseria, Streptococcus, Lactobacillus, Candida, Actinomyces will be used as positive controls and, V3-V4 and ITS regions will be matched for bacterial microbiota and Fungal microbiota.

Evaluation of Results

After the "Operational taxonomic units" of the amplicons are configured with the VSEARCH program, the analyzes will be carried out with GENBANK microbiota and micobiota data.

Recruitment and care of patients, collection of materials and management plan will be carried out by Perinatology team at Koç University Hospital Gynecology and Obstetrics Clinic during the study. The evaluation of materials will be carried out by the Department of Microbiology of Koç University, School of Medicine.

Only the research team will have access to the identity information of the participants. Only physicians in the perinatology department of Koç University Hospital, Department of Obstetrics and Gynecology, have access to the GE Voluson E8 Ultrasonography device and the hospital-approved Viewpoint archiving system, which is already in place at the Perinatology Department. After the research is completed, the forms will be destroyed by paper milling machine after 5 years.

The project is supported by TUBITAK (prot no: 119S463).

[figure not shown]

References:

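### The protocol defines the study group in two ways (about 18 women or all 60); under the narrower one, preterm birth cannot be separated from short cervix

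*Protocol*

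**What the plan says.** The protocol's Introduction states the hypothesis, about bacterial and fungal variety, in these terms: "pregnancies resulting in preterm birth are different than those who give birth at term although patients with sonographic short cervical length receive progesterone regularly". That implies a comparison of preterm with term birth among treated short-cervix women.

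The group definitions then diverge:

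- **Introduction.** "Study group will include women who had cervical length 25 mm or less" is the start of the definition. The same sentence adds a second condition, delivery before term: "or less than 25 mm at 20-24 th gestational week and underwent birth (preterm delivery) before 37 + 0 weeks of gestation". The next sentence sets this group against controls with a cervix above 25 mm and a term birth.
- **Study population.** Under the heading "The patients will be included in the study group", item 1 is "Pregnant women with cervical length of 25mm or less (n=60"), whatever the delivery outcome. Subgroup A is the 18 expected to deliver preterm. Subgroup B reads "B) Of 60 patients, almost 70% will be expected to give a birth at term (n=42").
- **Controls.** Item 2 of the same list agrees with the Introduction: "As a control group, women with a cervical length of more than 25 mm who give a birth at term will be included (n=32").

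The power statement in Study population says that enrolling 60 short-cervix women "would give the study a power of 85% to show a treatment effect at a two-sided alpha level of 5"%.

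The gestational window for classifying cervical length also varies: 20-24 weeks in the Introduction's group definition, 18-22 weeks in Study Procedure, and 18-24 weeks in the closing flow chart.

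**The concern.** Two readers of this protocol could analyse different study groups, one of about 18 women and one of 60.

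The narrower definition has the worse consequence. It leaves the short-cervix women who deliver at term in neither group: they did not deliver preterm, and their cervix is not above 25 mm. The only contrast left is short cervix with preterm birth against long cervix with term birth. Study Procedure starts progesterone only in women at 25 mm or less, so in samples taken after that point the two groups differ in treatment as well. A difference between them could reflect birth timing, cervical length or progesterone, and the hypothesis concerns only the first.

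A reader could also carry the 85% power over to the preterm comparison, which rests on about 18 women. For the 28- and 32-week swabs even 18 is an upper expectation. The Introduction says short-cervix women tend to deliver preterm especially at 20-28 weeks, and a woman who has delivered gives no later swab. Placental and neonatal samples come only from women followed and delivered at the hospital.

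**Working it through.** **Inputs (Protocol, Study population):** 60 women with cervical length of 25 mm or less; preterm risk 30% in that group; 32 long-cervix term controls; 1429 women screened; 85% power, two-sided 5%.

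**1. The protocol's own split.** 60 × 0.30 = 18 and 60 × 0.70 = 42. Both figures reproduce exactly.

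**2. Group membership under each definition.**

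| Women | Introduction | Study population |
|---|---|---|
| Short cervix, preterm (18) | study group | study group, A |
| Short cervix, term (42) | no group | study group, B |
| Long cervix, term (32) | control | control |

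The study group is 18 or 60. Under the Introduction, 42/60 = 70% of the short-cervix women are unassigned.

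**3. Which definition the screening number fits.** 60/1429 = 4.2%, and 60/0.042 = 1429 after rounding. At the same 4.2%, a study group of 18 would need 18/0.042 = 429 screened. The 1429 therefore goes with 60 women.

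**4. Can preterm birth and short cervix be separated?** Take a model with columns (intercept, preterm, short cervix).
- Introduction: 18 rows (1,1,1) and 32 rows (1,0,0). The last two columns are identical, so the rank is 2 of 3 and the two effects are not estimable separately.
- Study population: adding 42 rows (1,0,1) raises the rank to 3 of 3.

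**5. Uncertainty in the 18.** With preterm births distributed as Binomial(60, 0.30), the 2.5% and 97.5% quantiles are 11 and 25; P(11 to 25) = 0.967.

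**6. What the within-group comparison could detect (illustration only).** The protocol gives no microbiota effect size, so this assumes one continuous measure compared by a two-sample t test, two-sided 5%. The difference d, in SD units, solves P(T > t(0.975, n1+n2−2)) = 0.85, where T is noncentral t with noncentrality d/√(1/n1 + 1/n2).

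| Preterm v term, short cervix | d for 85% power |
|---|---|
| 18 v 42 (expected) | 0.86 SD |
| 25 v 35 | 0.80 SD |
| 11 v 49 | 1.02 SD |
| 14 v 42 (assumed loss of later samples) | 0.94 SD |
| 9 v 42 (assumed loss of later samples) | 1.12 SD |

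The counts 14 and 9 are assumptions to show a range; the protocol does not say how many preterm women will have each later sample.

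**The case against.** The strongest reply is that the heading in Study population is loose. It introduces the 60 short-cervix women and also the controls, so it may simply mean study population. On that reading the Introduction defines cases and controls, Study population lists everyone enrolled (18 + 42 + 32), and the only gap is that the role of the 42 is not named. The Introduction also says the group will include these women, which is softer than a strict limit, and nothing in the text says the 42 are dropped. Naming three groups would then be enough. The Introduction's stated aim, about women who had preterm birth due to a short cervix, also fits the narrower definition.

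Part of this stands. The heading is loosely worded, the 42 are enrolled, and the comparator the hypothesis needs therefore exists. The loss of identifiability is conditional on following the Introduction. It also applies to cervical length as the protocol uses it, cut at 25 mm. With measured length a model could be fitted, but with no overlap between the groups it would rest on functional form alone.

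The conflict is not removed. Within the list, item 1 is set against item 2, which is labelled as the control group, so item 1 is the study group. The same section ties the 1429 screened to recruiting the study group, and that number matches 60 women; the section later ties it to all the numbers listed, so this is supporting evidence only. The Introduction pairs its narrower group directly with the controls, so it reads as a complete comparison. No text reconciles the two. A statistical analysis plan may rank the contrasts, but it should not have to choose between two definitions in the protocol.

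**Conclusion.** The concern holds and should be fixed before analysis. The protocol gives two incompatible study groups, 18 or 60 women. Under the narrower one, 70% of the short-cervix women have no group and preterm birth is completely aliased with short cervix and, after treatment starts, with progesterone. Under the wider one, the comparison that the hypothesis implies is available at an expected 18 v 42. The defect is the conflicting definition, not a missing comparator.

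The 85% power should not be read as applying to either preterm comparison. It is stated for 60 women and a treatment effect, whereas all short-cervix women are to receive progesterone and the hypothesis concerns flora.

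The counts 18 and 42 rest on the protocol's 30% rate; chance alone gives 11 to 25 preterm births. The detectable differences of about 0.8 to 1.1 SD are illustrative and depend on an assumed continuous measure and, for the last two rows of the table, on assumed sample losses.

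**What to change.** 1. Use one definition throughout: the study group is all 60 women with cervical length of 25 mm or less. Amend the Introduction to match, and name the three sets of women (short cervix preterm, short cervix term, long cervix term) so that the role of the 42 is explicit.
2. State that the hypothesis is tested by preterm v term within the short-cervix group, expected 18 v 42, with a range of 11 to 25 preterm births.
3. Keep the 32 long-cervix term women as a secondary reference group. Say that contrasts against them in samples taken after treatment start are confounded by progesterone.
4. Withdraw the 85% figure, or restate it for 18 v 42 with the assumed effect and the number of preterm women expected to have each sample.
5. Reconcile the window for classifying cervical length across the Introduction, Study Procedure and the flow chart.

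This needs no extra women or samples, since the 42 are already planned as subgroup B. The cost is that short-cervix preterm v long-cervix term becomes a secondary contrast. The comparison that tests the hypothesis rests on about 18 preterm births, fewer for the 28- and 32-week swabs, so only large differences are detectable.

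### The aim concerns preterm birth caused by a short cervix, but the case group takes every birth before 37+0 and no provision is made for recording how birth began

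*Protocol*

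**What the plan says.** The Introduction gives the aim as describing the bacterial and fungal flora of "women who had preterm birth due to sonographic short cervical length". The background behind it concerns species said to predispose to premature labour when the cervix is short. The hypothesis, one sentence earlier, is broader. It says that "pregnancies resulting in preterm birth are different than those who give birth at term", among short-cervix women taking progesterone, and names no cause. The title names none either.

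The paragraph before the inclusion criteria makes a woman a case if her cervical length is 25 mm or less and she "underwent birth (preterm delivery) before 37 + 0 weeks of gestation". The comparison group is given there as: "The control group had pregnancies with a cervical length above 25 mm and delivered at term (37 + 0 gestational week and above". The Study population section counts cases the same way. Of 60 short-cervix women, "30% will be expected to give a birth before 37 gestational weeks (n=18", and 42 are expected to deliver at term. There are 32 controls with a longer cervix.

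The exclusions nearest to this point are fetal anomaly and fetal death ("Finding the intrauterine mort de fetus"). Delivery started for a maternal or fetal indication is not excluded. No section requires spontaneous onset or provides for recording it. Apart from a title in the reference list, the word spontaneous does not occur.

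**The concern.** A woman with a short cervix may be delivered before 37+0 because of maternal disease or fetal compromise. She meets the case definition, yet the birth need not have come about through her cervix or her flora. If such women resemble those who deliver at term, including them shrinks the preterm-versus-term contrast. If they have a flora of their own, for example through the maternal disease or its treatment, the contrast can move in either direction.

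With only 18 cases expected, an indicated share of 10–40% would mean about 2 to 7 women, enough to alter the result. Unless onset of birth is captured, a later analysis plan cannot readily separate the two kinds of case. The case definition is fixed in the protocol itself, so this is not a detail that a statistical analysis plan would normally settle.

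**Working it through.** **Inputs from the protocol.** 60 short-cervix women; preterm risk 30%; 32 long-cervix term controls; 85% power; two-sided 5% level.

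**Inputs assumed, because the protocol gives none.**
- q: the provider-initiated share of the preterm cases, taken as 10%, 20%, 30% and 40%.
- r: the share of the spontaneous-preterm contrast that provider-initiated cases carry (0 = they look like the comparator, 1 = they look like spontaneous cases).
- d: the contrast in SD units on some continuous microbiota measure, set so that the planned groups have exactly 85% power.

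**Step 1, the plan's own figures.** 0.30 × 60 = 18 and 0.70 × 60 = 42, so the split reproduces. The power statement ("would give the study a power of 85% to show a treatment effect") names no microbiota endpoint or effect size. Read as 30% v 12%, the only two rates given, it is not reproduced: power is 68% for 60 v 60 and 49% for 60 v 32, and 85% needs 91 per group. That is a separate matter. Here 85% serves only as an anchor.

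**Step 2, anchor.** Two-sample t-test, noncentral t distribution. For 18 v 42 the standard error is √(1/18 + 1/42) = 0.2817. Power of 85% on 58 degrees of freedom needs d = 0.858.

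**Step 3, formulas.**
- All births before 37+0 as cases: difference = d × [1 − q(1 − r)]; case variance = 1 + q(1 − q)(1 − r)²d², pooled with the comparator variance of 1.
- Spontaneous births only: 18(1 − q) v 42, difference d, variance 1.

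**Step 4, one line in full (q = 30%).**
- All births, r = 0: difference 0.858 × 0.70 = 0.601; case variance 1 + 0.21 × 0.858² = 1.155; pooled variance (17 × 1.155 + 41)/58 = 1.045; standard error √(1.045 × 0.0794) = 0.288; noncentrality 0.601/0.288 = 2.09; power 54%.
- Spontaneous only: 12.6 v 42; standard error √(1/12.6 + 1/42) = 0.321; noncentrality 0.858/0.321 = 2.67; power 75%.
- All births, r = 0.75: difference 0.858 × 0.925 = 0.794; power 79%.

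**Step 5, results for 18 preterm v 42 term, all with a short cervix.**

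| q | Spontaneous cases | Power, spontaneous only | Power, all births, r = 0 | Power, all births, r = 0.75 | Break-even r |
|---|---|---|---|---|---|
| 10% | 16.2 | 82% | 76% | 83% | 0.64 |
| 20% | 14.4 | 79% | 65% | 81% | 0.62 |
| 30% | 12.6 | 75% | 54% | 79% | 0.60 |
| 40% | 10.8 | 69% | 42% | 77% | 0.57 |

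Below the break-even r, restricting to spontaneous births has more power; above it, the all-cause group does. At r = 1 the all-cause group keeps its 85%.

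**Step 6, against the 32 long-cervix controls.** The same method gives d = 0.90 SD and a break-even r of about 0.67 to 0.60 as q rises from 10% to 40%. A value of r near 0 is less plausible here. Provider-initiated cases still have a short cervix and, under the Study Procedure, progesterone, so they differ from these controls whatever started the birth.

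**The case against.** The strongest reply is that the inconsistency rests on the words 'due to' in one sentence. The title and hypothesis speak of preterm birth without a cause, and the two operational passages apply one consistent definition. On that reading the aim is loosely worded and the case group is what was meant. This stands in part. A reader might infer that the plan answers a different question from the one it set out to ask. The documents do not support that: the definition fits the title and hypothesis, and departs from the aim and from the premature-labour rationale. Two targets are stated, and the protocol does not choose between them.

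The second reply concerns power, and it stands. A reader might infer that counting provider-initiated births always dilutes the contrast, so that restriction is free of any trade-off. That holds only when r is low. The documents say nothing about r, and above the break-even values the all-cause group has more power. Even then, the extra power is for the all-cause contrast, not for the one named in the aim.

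Third, q, r and d are all assumed, so the figures show what would follow from the assumptions and not what this study will lose. That is correct, and the reconciliation does not rest on them.

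Fourth, the same team handles follow-up and delivery, so onset may be available from clinical records, and sensitivity analyses may be left to an analysis plan. Both are fair. However, nothing in the protocol secures the record, and the protocol itself fixes who is a case.

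**Conclusion.** The concern holds in a limited form. The aim is cause-specific, the case definition and the count of 18 are all-cause, and no provision is made for recording how birth began. These passages need to be reconciled.

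The size of the consequence cannot be read from the documents. For a contrast detectable with 85% power at 18 v 42, and with 10–40% of cases provider-initiated, the all-cause group has 76–42% power against 82–69% for spontaneous cases if provider-initiated births look like term births. It has 83–77% if they carry three-quarters of the contrast. The crossing point is r of about 0.64–0.57, or 0.67–0.60 against the 32 controls, where a low r is also less likely. If provider-initiated births have a flora of their own, bias can go either way.

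The case for change is therefore that it aligns the main comparison with the stated aim at little cost. It is not that power is certain to improve. This should be changed; confidence is medium.

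**What to change.** 1. Record onset of birth for every woman on the birth form: spontaneous labour or membrane rupture, or provider-initiated.
2. In the study-group paragraph and in group 1A, define the main case group as spontaneous birth before 37+0 in a woman with cervical length of 25 mm or less. Bring the aim and hypothesis into line with that wording.
3. Report provider-initiated preterm births as a separate category, outside both sides of the main comparison. Give the all-preterm comparison as a sensitivity analysis.
4. Label n=18 as all-cause and state the smaller expected spontaneous number beside it: 18 × 0.9 to 18 × 0.6, about 16 to 11, if 10–40% are provider-initiated.

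The cost is one form field and some rewording, with no extra women or samples. The downside is fewer cases in the main comparison, and some loss of power if provider-initiated births resemble spontaneous ones. Keeping 18 spontaneous cases would be a different and larger change: 18/[0.30 × (1 − q)] is about 67 to 100 short-cervix women instead of 60. It is not needed to resolve this point.

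### The whole-pregnancy exclusion for antibiotic or antifungal use drops women already enrolled and sampled; limiting it to use before the first swab would keep their unexposed swabs and outcomes

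*Protocol*

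**What the plan says.** The exclusion list after the Introduction contains "Antibiotic and / or antifungal use at any time of pregnancy". No other part of the protocol limits this criterion to a period before enrolment or before sampling. The Introduction, just ahead of the inclusion criteria, also says: "During the follow-up of pregnancies, care will be taken not to use antibiotics". That sentence names antibiotics only and has no clause on clinical need.

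Under Study Procedure, "vaginal swabs of women who accept to participate in the study will be collected at 11-14th weeks of gestation". A second swab follows at 18-22 weeks, and cervical length is measured again "at 28th and 32nd gestational weeks, and samples will be taken with vaginal swab before these measurements". Placental tissue and a neonatal buccal swab are taken at birth; the Introduction limits these to women followed and delivered in the study hospital.

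Study population plans for 60 short-cervix women, of whom 30% (18) are expected to deliver preterm, and states: "For the recruitment of study group, 1429 women with singleton pregnancies will need to be screened". The closing text of Evaluation of Results says: "Recruitment and care of patients, collection of materials and management plan will be carried out by Perinatology team".

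**The concern.** Keeping drug-exposed flora out of a microbiome comparison is a sensible aim. The difficulty is the unit on which the rule acts: the whole woman over the whole pregnancy, not the exposed sample. A woman who joins at 11-14 weeks can become ineligible at any later date. A course begun after the 32-week swab excludes her although all her vaginal swabs were taken before it. The same list handles bleeding differently: it counts only if present when the swab is taken. A criterion tied to sampling was therefore within the protocol's own approach.

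At stake are usable early swabs and outcomes in a small key group. There is also a lesser matter of conduct. The team that recruits also treats, and under this rule treating a participant costs the study that participant. It is better to state that treatment decisions do not depend on the study than to leave it to be understood.

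**Working it through.** **Inputs, all from the protocol.** Vaginal swabs at 11-14, 18-22, 28 and 32 weeks, and placental and buccal samples at birth (Study Procedure); 60 short-cervix women, 30% preterm, 1429 screened (Study population).

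**The protocol's own figure.** 0.30 × 60 = 18 expected preterm births, which reproduces.

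**Samples scheduled**, for a woman who reached the 18-22 week visit and delivers in the study hospital:
- delivery before 28 weeks: 2 vaginal + 2 at birth = 4
- delivery from 28 to before 32 weeks: 3 + 2 = 5
- delivery at 32 weeks or later: 4 + 2 = 6

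**Samples before and after a course.** After = scheduled − before.

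| Course falls | Before | After, delivery <28 wk | After, delivery 28 to <32 wk | After, delivery ≥32 wk |
|---|---|---|---|---|
| between the 11-14 and 18-22 wk visits | 1 | 4 − 1 = 3 | 5 − 1 = 4 | 6 − 1 = 5 |
| between 18-22 and 28 wk | 2 | 4 − 2 = 2 | 5 − 2 = 3 | 6 − 2 = 4 |
| between 28 and 32 wk | 3 | – | 5 − 3 = 2 | 6 − 3 = 3 |
| after 32 wk | 4 | – | – | 6 − 4 = 2 |

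The exclusion therefore removes 1 to 4 unexposed vaginal swabs per treated woman, together with her outcome. The exposed samples number 2 to 5. For a woman who delivers elsewhere there are no birth samples, so each after-course count falls by 2 (range 0 to 3) and the before-course counts do not change. The count of four vaginal swabs rests on Study Procedure; the flow chart shows a single box for 28-32 weeks.

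**Weight of one case.** 1/18 = 5.6% of the expected preterm group.

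**Replacement, as an illustration only.** 1429/60 = 23.8 women screened per short-cervix woman, and 23.8/0.30 = 1429/18 = 79.4 per expected preterm case. This assumes that the 60 and 18 are counted before the exclusion is applied, which the protocol does not say.

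**Number affected.** The protocol gives no treatment rate. If 10%, 20% or 30% of women were treated after enrolment, equally in preterm and term births, the expected 18 would become 18 × 0.9 = 16.2, 18 × 0.8 = 14.4 or 18 × 0.7 = 12.6. These rates are assumptions chosen to show a range, not estimates.

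**The case against.** The case for the present rule has real force.

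- **Groups are defined by delivery outcome and samples are frozen until evaluated.** The analysed set is fixed only after birth, and fetal death, in the same list, can also arise after the first swab. This explains how a late exclusion can be operated. It does not show why swabs taken before the drug should be lost.
- **Placental and neonatal flora are part of the aim.** A course after 32 weeks comes before both, and restriction to untreated pregnancies keeps each woman's set unexposed throughout. This stands, and is why the exposed birth samples should stay out of the main flora analysis.
- **An early swab is unexposed, but its link to outcome may not be.** Treatment falls between swab and delivery, and the Introduction itself suggests that treating flora changes might reduce preterm birth. This also stands. It calls for an untreated-only sensitivity analysis beside the fuller set, which shows both and loses nothing.
- **Handling of exposed samples can be left to an SAP.** True, and none is shown. Eligibility, however, is a protocol matter, and this criterion is already fixed.

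Two stronger readings are tempting. A reader might infer that indicated antibiotics are withheld from participants. The text does not support this: taking care to avoid a drug is not a ban, antifungals are not mentioned in that sentence, and the consent pages, which might contain a usual-care statement, are not in the file. A reader might also infer that the exclusion biases the association between flora and preterm birth, because treatment could be commoner in pregnancies that end early. The protocol gives no treatment rates overall or by outcome, so neither the direction nor the size of such an effect can be derived. Nor does it say that stored samples from excluded women are destroyed.

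**Conclusion.** The point holds as a minor, inexpensive improvement to a stated rule. Read literally, the criterion excludes women already enrolled because of a later event, and takes 1 to 4 pre-course vaginal swabs and the outcome of each out of the comparison. Each expected preterm case lost is 5.6% of that group; the total loss is unknown. This rests on three things: that the criterion means what it says for the whole pregnancy, that the visit schedule is the one in Study Procedure, and that the woman reached the 18-22 week visit. The sentence on avoiding antibiotics warrants a clarification and nothing more.

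**What to change.** 1. Reword the criterion to exclude antibiotic or antifungal use in the current pregnancy before the 11-14 week swab.
2. For later courses, record agent, indication, and start and stop dates.
3. Keep later-treated women with their outcome and all samples taken before the course. Leave post-exposure vaginal, placental and neonatal samples (the last two where collected) out of the main flora analysis.
4. Repeat the analysis in untreated pregnancies only, as a sensitivity analysis.
5. Replace the sentence on antibiotics in follow-up with one saying that unnecessary use is avoided and that clinically indicated antibiotic or antifungal treatment is given regardless of participation.

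The cost is one reworded criterion, one replaced sentence, a short medication record on the case report form and one extra analysis. Treated women will contribute incomplete sample sets; under the present rule they contribute none.
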